# Better BP Study

## Study Visit 3 Data Collection Form

ID: \_\_\_\_\_

Date of Visit: \_\_\_\_\_

Name of tech performing visit: \_\_\_\_\_

Time of Visit: \_\_\_\_\_

### **BEFORE PARTICIPANT ARRIVES**

4. Verify cuffs of various sizes are available for the WatchBP O3 and WatchBP Home N:

### **AFTER PARTICIPANT ARRIVES**

#### **IF PARTICIPANT COMPLETED THE HBPM DEVICE FIRST**

1. Check a complete recording (i.e. – two sleep BP readings) was obtained.
  - a. Yes      No
2. If yes, complete the post-HBPM questionnaire.
3. If no, ask the participant to repeat the HBPM. Discuss with participant the challenges they encountered with obtaining a complete HBPM.
4. Ask participant what time he/she anticipates going to sleep tonight and waking up tomorrow
  - a. Anticipated time going to sleep: \_\_\_\_\_
  - b. Anticipated time waking up tomorrow: \_\_\_\_\_

5. Initialize ABPM device. Serial number: \_\_\_\_\_

6. Is the participant's non-dominant arm being used for the WatchBP O3 ABPM?      Yes      No

7. Reason for not using the non-dominant arm: \_\_\_\_\_

a. Put "X" next to cuff sizes that will be used

		ABPM (Microlife WatchBP O3)	
Cuff Size	Arm circumference	Dominant arm	Non-dominant arm
Small adult	17-21.9 cm		
Med adult	22-32 cm		
Large adult	32.1-42 cm		
Extra-large	42.1-52 cm		

8. Place cuff on arm

- a. Find brachial artery (perhaps make small mark)
- b. Arrow on cuff over brachial artery, non-latex tubing coming out of cuff top
- c. Bottom of cuff 1" above bend/crease in elbow (if possible)
- d. Equal tension top and bottom of cuff (1 finger easily, 2 fingers snug, top and bottom)
- e. Wrap grey non-latex tubing around back of neck

9. Connect tubing to ABPM device (make sure it will not pull out)
10. Place the O3 device in 'Ambulatory' mode.
11. Explain to participant about importance of remaining still during readings and keeping arm a) relaxed at side or in a "sling-like" position if standing, b) resting on table, arm rest, bed, etc. if sitting/reclining
12. Take one test reading; repeat until obtain a valid reading (max 5 tries)
  - a. If cannot get a valid reading, check for cuff too loose, kink in tubing, tubing not securely connected to ABPM device; if need be, change cuff and/or ABPM device (be sure to record new serial #)
  - b. After getting a good reading, wait 30 secs, then start another reading & immediately cancel it
13. Decide if participant will use shoulder strap (preferred), Microlife belt, own belt, or jacket pocket. Instrument ABPM cover appropriately, insert ABPM in cover, and make sure participant is comfortable with this method of wearing device.
14. Review ABPM device log with participant (and remind them to bring it tomorrow or their next study visit)
15. If the participant intends to remove the device to shower/changes clothes, require the participant to practice placing the device correctly with you present.
16. Review with participant:
  - a. Importance of remaining still when BP readings are being taken
  - b. Importance of keeping arm relaxed/supported
  - c. If there is a failed reading, device will attempt three (3) retries ~1 minute apart
  - d. If participant is consistently getting 2 failed readings, should call study cellphone
  - e. ABPM cannot get wet
  - f. If they intend to remove the device at any point, please do so between readings
  - g. Payment depends on getting 80% successful readings

## **IF PARTICIPANT COMPLETED THE ABPM DEVICE FIRST**

17. Check a complete recording (i.e. ~35 BP measurements) was obtained.
  - a. Yes      No
18. If yes, complete the post-ABPM questionnaire.
19. If no, ask the participant to repeat the ABPM. Discuss with participant the challenges they encountered with obtaining a complete ABPM.
20. Ask participant what time he/she anticipates going to sleep tonight and waking up tomorrow
  - a. Anticipated time going to sleep: \_\_\_\_\_
  - b. Anticipated time waking up tomorrow: \_\_\_\_\_
21. Initialize HBPM device. Serial number: \_\_\_\_\_
22. Is the participant's non-dominant arm being used for the WatchBP Home N? Yes      No
23. Reason for not using the non-dominant arm: \_\_\_\_\_
  - a. Put "X" next to cuff sizes that will be used

		HBPM (Microlife WatchBP Home N)	
Cuff Size	Arm circumference	Dominant arm	Non-dominant arm
Small adult	17-21.9 cm		
Med adult	22-32 cm		
Large adult	32.1-42 cm		
Extra-large	42.1-52 cm		
24. Demonstrate to the participant how to place the cuff on their arm
  - a. Find brachial artery (perhaps make small mark)
  - b. Arrow on cuff over brachial artery, non-latex tubing coming out of cuff top
  - c. Bottom of cuff 1" above bend/crease in elbow (if possible)
  - d. Equal tension top and bottom of cuff (1 finger easily, 2 fingers snug, top and bottom)
  - e. Wrap grey non-latex tubing around back of neck
  - f. Connect tubing to HBPM device (make sure it will not pull out)
25. Allow the participant to practice placing the cuff on their arm with you present.
26. Explain to participant the importance of placing the device correctly and initializing the device when they get in bed by holding the on/off button for 3 seconds to start the initial reading and the following readings will occur 2, 3, and 4 hours after they have gone to bed.
27. Take one test reading in 'Usual' mode; repeat until obtain a valid reading (max 3 tries)
  - a. If cannot get a valid reading, check for cuff too loose, kink in tubing, tubing not securely connected to HBPM device; if need be, change cuff and/or HBPM device (be sure to record new serial #)
28. Place the device in 'Nocturnal' mode.
29. Place the device in a carrier bag for the participant.
30. Review with participant:
  - a. Importance of initializing the device before going to bed by holding the on/off button for 3 seconds
  - b. If there is a failed reading, device will attempt three (3) retries ~1 minute apart

- c. If participant is consistently getting 2 failed readings while initializing the device, they should call the study cellphone
- d. Payment depends on getting three successful readings while asleep

31. Answer any questions that the participant may have.

NOTES: \_\_\_\_\_

## **Better BP Study Visit 4 Checklist**

[ ] COVID-19 Screening [ ] Yes [ ] No

[ ] Symptom Tracker

[ ] Temperature Check

[ ] Device return

[ ] Check the device for complete readings

[ ] HBPM two sleep BP readings [ ] Yes [ ] No

[ ] ABPM ~35 measurements [ ] Yes [ ] No

[ ] Actiwatch to be remove at this visit

If No, ask participant to wear the device again to collect all necessary readings or measurements.

If yes, complete the following questionnaires

**(circle one:** email or in-person)

[ ] Post ABPM Questionnaire [ ] Trait Anxiety Index

[ ] Post HBPM Questionnaire [ ] Expectations of Outcomes

[ ] Comparability Questionnaire

[ ] Collect non-fasting blood work

[ ] Biospecimens [ ] Urine sample

[ ] Genetic sample

[ ] Echocardiogram

Completed by \_\_\_\_\_

Date \_\_\_\_\_

# Better BP Study

## Study Visit 4 Data Collection Form

ID: \_\_\_\_\_

Date of Visit: \_\_\_\_\_

Name of tech performing visit: \_\_\_\_\_

Time of Visit: \_\_\_\_\_

### **AFTER PARTICIPANT ARRIVES**

32. Participant will return the device and device log for you to check for completion.
33. Check a complete recording (i.e. – two sleep BP readings or ~35 ABPM readings) was obtained.
  - a. Yes      No
34. If yes, complete the post-HBPM or post-ABPM questionnaire.
35. If no, ask the participant to repeat the HBPM or ABPM. Discuss with participant the challenges they encountered with obtaining a complete HBPM or ABPM.
36. Participant will complete the post-HBPM questionnaire or post-ABPM questionnaire.
37. Complete a non-fasting blood draw
38. Collect a spot urine collection.
39. Take the participant to complete their echocardiogram or schedule them for an echocardiogram within the next 2 weeks.
40. Please confirm the participant's mailing address.
41. Remind the participant that they will:
  - a. Be compensated for all 4 study visits within 2-3 weeks following their echocardiogram
  - b. Receive their 24-hour ABPM report, labs and echocardiogram results in the mail
  - c. We may contact them in the future for additional studies if they have consented to be contacted
42. Answer any questions that the participant may have.

NOTES: \_\_\_\_\_

---

---

---

---

---

---

## **Sociodemographic and Medical History Questionnaire**

1. What is your age? \_\_\_\_\_
  
2. What is your date of birth? \_\_\_\_\_\\_\_\_\_\_\\\_\_\_\_\_
  
3. Are you Hispanic?
  - a. Yes
  - b. No
  - c. Decline to respond
  
4. What is your race?
  - a. White
  - b. Black
  - c. American Indian/Alaska Native
  - d. Asian
  - e. Native Hawaiian or Other Pacific Islander
  - f. More than one race
  - g. Decline to respond
  
5. What is your sex?
  - a. Male
  - b. Female
  
6. What is your highest level of education completed?
  - a. Less than high school
  - b. High school diploma or equivalency
  - c. Some college
  - d. Bachelor's degree
  - e. Graduate degree
  
7. What is your combined annual household income?
  - a. < \$25,000
  - b. \$25,000 to \$49,999
  - c. \$50,000 to \$74,999
  - d. \$75,000 or greater

8. What is your marital status?

- a. Single
- b. Married
- c. Separated
- d. Divorced
- e. Widowed

9. Are you living alone?

- a. Yes
- b. No

10. Have you ever been told by a doctor or a health professional that you have any of the following? Check those to which the answer is yes (leave other blank).

- High blood pressure or hypertension (excluding during pregnancy)
- High cholesterol
- Diabetes
- Asthma or hay fever

11. Have you smoked 100 cigarettes in your lifetime?

- a. Yes
- b. No

12. If you answered 'Yes' to Q11, do you smoke cigarettes now, even occasionally?

- a. Yes
- b. No

13. How many times per week do you engage in intense physical activity, enough to work up a sweat? \_\_\_\_\_

14. Do you presently drink alcoholic beverages, including beer, wine, and other drinks made with hard liquor, even occasionally?

- a. Yes
- b. No

If yes, how many alcoholic beverages do you drink during an average week?

## Pittsburg Sleep Quality Index

Instructions: The following questions relate to your usual sleep habits during the past month only. Your answers should indicate the most accurate reply for the majority of days and nights in the past month. **Please answer all questions.**

1. During the past month, what time have you usually gone to bed at night? \_\_\_\_\_
2. During the past month, how long (in minutes) has it usually taken you to fall asleep each night? \_\_\_\_\_
3. During the past month, what time have you usually gotten up in the morning? \_\_\_\_\_
4. During the past month, how many hours of actual sleep did you get at night? (This may be different than the number of hours you spent in bed.) \_\_\_\_\_

5. During the past month, how often have you had trouble sleeping because you...	Not during the past month	Less than once a week	Once or twice a week	Three or more times a week
a. Cannot get to sleep within 30 minutes				
b. Wake up in the middle of the night or early morning				
c. Have to get up to use the bathroom				
d. Cannot breathe comfortably				
e. Cough or snore loudly				
f. Feel too cold				
g. Feel too hot				
h. Have bad dreams				
i. Have pain				
j. Other reason(s), please describe:				
6. During the past month, how often have you taken medicine to help you sleep (prescribed or "over the counter")?				
7. During the past month, how often have you had trouble staying awake while driving, eating meals, or engaging in social activity?				
	No problem at all	Only a very slight problem	Somewhat of a problem	A very big problem
8. During the past month, how much of a problem has it been for you to keep up enough enthusiasm to get things done?				
	Very good	Fairly good	Fairly bad	Very bad

9. During the past month, how would you rate your sleep quality overall?				
	No bed partner or roommate	Partner/roommate in other room	Partner in same room but not same bed	Partner in same bed
10. Do you have a bed partner or roommate?				
	Not during the past month	Less than once a week	Once or twice a week	Three or more times a week
If you have a roommate or bed partner, ask him/her how often in the past month you have had:				
a. Loud snoring				
b. Long pauses between breaths while asleep				
c. Legs twitching or jerking while you sleep				
d. Episodes of disorientation or confusion during sleep				
e. Other restlessness while you sleep, please describe:				

## Scoring the PSQI

The order of the PSQI items has been modified from the original order in order to fit the first 9 items (which are the only items that contribute to the total score) on a single page. Item 10, which is the second page of the scale, does not contribute to the PSQI score.

In scoring the PSQI, seven component scores are derived, each scored 0 (no difficulty) to 3 (severe difficulty). The component scores are summed to produce a global score (range 0 to 21). Higher scores indicate worse sleep quality.

### Component 1: Subjective sleep quality—question 9

Response to Q9	Component 1 score
Very good	0
Fairly good	1
Fairly bad	2
Very bad	3

Component 1 score: \_\_\_\_\_

### Component 2: Sleep latency—questions 2 and 5a

Response to Q2	Component 2/Q2 subscore
< 15 minutes	0
16-30 minutes	1
31-60 minutes	2
> 60 minutes	3

Response to Q5a	Component 2/Q5a subscore
Not during past month	0
Less than once a week	1
Once or twice a week	2
Three or more times a week	3

Sum of Q2 and Q5a subscores	Component 2 score
0	0
1-2	1
3-4	2
5-6	3

Component 2 score: \_\_\_\_\_

### Component 3: Sleep duration—question 4

Response to Q4	Component 3 score
> 7 hours	0
6-7 hours	1
5-6 hours	2
< 5 hours	3

Component 3 score: \_\_\_\_\_

**Component 4: Sleep efficiency—questions 1, 3, and 4**

Sleep efficiency = (# hours slept/# hours in bed) X 100%

# hours slept—question 4

# hours in bed—calculated from responses to questions 1 and 3

Sleep efficiency	Component 4 score
> 85%	0
75-84%	1
65-74%	2
< 65%	3

Component 4 score: \_\_\_\_\_

**Component 5: Sleep disturbance—questions 5b-5j**Questions 5b to 5j should be scored as follows:

Not during past month	0
Less than once a week	1
Once or twice a week	2
Three or more times a week	3

Sum of 5b to 5j scores	Component 5 score
0	0
1-9	1
10-18	2
19-27	3

Component 5 score: \_\_\_\_\_

**Component 6: Use of sleep medication—question 6**

Response to Q6	Component 6 score
Not during past month	0
Less than once a week	1
Once or twice a week	2
Three or more times a week	3

Component 6 score: \_\_\_\_\_

**Component 7: Daytime dysfunction—questions 7 and 8**

Response to Q7	Component 7/Q7 subscore
Not during past month	0
Less than once a week	1
Once or twice a week	2
Three or more times a week	3

Response to Q8	Component 7/Q8 subscore
No problem at all	0
Only a very slight problem	1
Somewhat of a problem	2
A very big problem	3

Component 7 score: \_\_\_\_\_

**Global PSQI Score:** Sum of seven component scores: \_\_\_\_\_

Copyright notice: The Pittsburgh Sleep Quality Index (PSQI) is copyrighted by [name]. Permission has been granted to reproduce the scale on this website for clinicians to use in their practice and for researchers to use in non-industry studies. For other uses of the scale, the owner of the copyright should be contacted.

Citation: Buysse, DJ, Reynolds CF, Monk TH, Berman SR, Kupfer DJ: The Pittsburgh Sleep Quality Index (PSQI): A new instrument for psychiatric research and practice. *Psychiatry Research* 28:193-213, 1989

5b. If you did not answer 'Not at all' in question 5a, did the noise of the monitor bother you... (Check all that apply):

At home

At work

While driving

At other times

## 6. Did the noise of the monitor disturb others?

7. Did you find the monitor embarrassing to wear?

8. Did you find the monitor interfered with your normal sleeping pattern?

No \_\_\_\_\_ Yes \_\_\_\_\_

9a. If you answered 'Yes' to Q8, how much was your sleep disturbed?

9b. If your sleep was disturbed, did the monitor wake you up after you had fallen asleep?

No \_\_\_\_\_ Yes \_\_\_\_\_

10. Did the monitor disturb you so much that you removed it during the day while awake?

No \_\_\_\_\_ Yes \_\_\_\_\_

11. Did the monitor disturb you so much during the night while asleep that you removed it?

No \_\_\_\_\_ Yes \_\_\_\_\_

12. How much pain did you experience while wearing the monitor?

13. How much irritation did you experience while wearing the monitor?

14. How much bruising did you experience while wearing the monitor?

# Post-sleep Blood Pressure Monitoring Questionnaire

For the following questions, please circle the answer that corresponds to your response on a scale from “Not at all” to “A lot”:

## 1. Did you find the monitor heavy?

2. Did you find the monitor comfortable to wear?

3. Did you find the monitor straightforward to use?

4. Did you find the monitor cumbersome or awkward to wear?

5. Did the noise of the monitor disturb you?

## 6. Did the noise of the monitor disturb others?

7. Did you find the monitor embarrassing to wear?

8. Did you find the monitor interfered with your normal sleeping pattern?

No Yes

9a. If you answered 'Yes' to Q8, how much was your sleep disturbed?

A little A moderate amount A lot

9b. If your sleep was disturbed, did the monitor wake you up after you had fallen asleep?

No Yes

10. Did the monitor disturb you so much during the night that you removed it?

No Yes

11. How much pain did you experience while wearing the monitor?

None A little A moderate amount A lot

12. How much irritation did you experience while wearing the monitor?

None A little A moderate amount A lot

13. How much bruising did you experience while wearing the monitor?

None A little A moderate amount A lot

## Comparability questionnaire

Ambulatory blood pressure monitoring involves wearing a device that measures blood pressure every 30 minutes during a 24-hour period. Home blood pressure monitoring involves you taking your own two blood pressure measurements in the morning and two blood pressure measurements in the evening, each day for one week (a total of 28 blood pressure measurements).

1. If your doctor thought it would be helpful to have information about what your blood pressure was during sleep,

- a. How willing would you be to perform a 24-hour ambulatory blood pressure recording?

0 Not at all willing	1 A little willing	2 Moderately willing	3 Very willing	4 Completely willing
----------------------------	--------------------------	----------------------------	----------------------	----------------------------

- b. How willing would you be to wear the home blood pressure monitor for one night?

0 Not at all willing	1 A little willing	2 Moderately willing	3 Very willing	4 Completely willing
----------------------------	--------------------------	----------------------------	----------------------	----------------------------

2. If your doctor thought it would be helpful to have information about what your blood pressure was outside the clinic,

- a. How willing would you be to perform a 24-hour ambulatory blood pressure recording?

0 Not at all willing	1 A little willing	2 Moderately willing	3 Very willing	4 Completely willing
----------------------------	--------------------------	----------------------------	----------------------	----------------------------

- b. How willing would you be to perform home blood pressure monitoring for a week?

0 Not at all willing	1 A little willing	2 Moderately willing	3 Very willing	4 Completely willing
----------------------------	--------------------------	----------------------------	----------------------	----------------------------

3. Which device would you prefer to wear if you had to repeat this study?
  - a. Ambulatory blood pressure monitor
  - b. Home blood pressure monitor
  - c. Neither

## State Anxiety Questionnaire

[figure not shown]
[figure not shown]
Better BP  
Spielberger's State Anxiety Inventory

Study ID

Directions: Read each statement below and then mark the appropriate circle to the right of the statement to indicate how you generally feel. There are no right or wrong answers. Do not spend too much time on any one statement but give the answer which seems to describe how you generally feel.

	Not at all	Somewhat	Moderately so	Very Much So
1. I feel calm				
2. I feel secure				
3. I feel tense				
4. I feel strained				
5. I feel at ease				
6. I feel upset				
7. I am presently worrying over possible misfortunes				
8. I feel satisfied				
9. I feel frightened				
10. I feel comfortable				
11. I feel self-confident				
12. I feel nervous				
13. I am jittery				
14. I feel indecisive				
15. I feel relaxed				
16. I feel content				
17. I feel worried				
18. I feel confused				
19. I feel steady				
20. I feel pleasant				

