## Better BP Supplement

### Questionnaire Administration

1. **State Anxiety Index** (Prior to unattended and attended blood pressure measurements at visits 1 and 2 [based on randomization order]; during night of ABPM and HBPM)
2. **Trait Anxiety Index** (At visit 4 – optional to administer electronically)
3. **Expectations of Outcomes** (At visit 4 - optional to administer electronically)

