### Examples of Questionnaire Administration

If participant is randomized to Unattended→Attended and ABPM → HBPM, please administer the questionnaires in the following order:

Visit 1	Visit 2	Visit 3	Visit 4
After office BP randomization, the state anxiety inventory will be administered unattended in concordance with the first clinic BP measurement.	After office BP randomization, the state anxiety inventory will be administered attended in concordance with the first clinic BP measurement.		After participants complete the device satisfaction questionnaire, the trait anxiety questionnaire and expectations of outcomes survey will be completed.
	After ABPM or home randomization, the state anxiety inventory will be completed at bedtime on the night of ABPM	After ABPM or home randomization, the state anxiety inventory will be completed at bedtime on the night of HBPM	

Unattended = give the participant the questionnaire and leave the room for 5 minutes

Attended = give the participant the questionnaire and remain in the room while they complete it

If participant is randomized to Attended→Unattended and HbPM → ABPM, please administer the questionnaires in the following order:

[figure not shown]
Visit 1	Visit 2	Visit 3	Visit 4
After office BP randomization, the state anxiety inventory will be administered attended in concordance with the first clinic BP measurement.	After office BP randomization, the state anxiety inventory will be administered unattended in concordance with the first clinic BP measurement.		After participants complete the device satisfaction questionnaire, the trait anxiety questionnaire and expectations of outcomes survey will be completed.
	After ABPM or home randomization, the state anxiety inventory will be completed at bedtime on the night of HbPM	After ABPM or home randomization, the state anxiety inventory will be completed at bedtime on the night of ABPM	

Unattended = give the participant the questionnaire and leave the room for 5 minutes

Attended = give the participant the questionnaire and remain in the room while they complete it

[figure not shown]

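### The printed state anxiety form carries the trait form's directions, so it does not ask about the moment of measurement and is likely to understate differences between conditions

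*Combined protocol and SAP*

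**What the plan says.** The manual's Better BP Supplement, under Questionnaire Administration, schedules the state form as follows: "Prior to unattended and attended blood pressure measurements at visits 1 and 2 [based on randomization order]; during night of ABPM and HBPM". The section on examples of questionnaire administration ties each completion to a condition. One clinic form is filled in alone and the other with staff present ("Attended = give the participant the questionnaire and remain in the room while they complete it"). The remaining two are filled in at bedtime, one on the ABPM night and one on the HBPM night. REDCap lists four state instruments, V1 to V4, which matches that count.

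The trait form is given once: "At visit 4 – optional to administer electronically".

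The printed State Anxiety Questionnaire opens by asking the participant to "indicate how you generally feel" and closes by asking them to "give the answer which seems to describe how you generally feel". The Trait Anxiety Questionnaire prints the same directions.

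**The concern.** A state scale given once per condition is useful only if answers can move with the condition. Directions that ask about general feeling set a time frame that does not move. The four completions then lean towards repeating a stable characteristic, and any true difference between conditions is pulled towards zero.

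The study asks whether an observer's presence changes the reading, and whether one monitor is easier to live with than another. A finding of no difference in state anxiety could be offered as evidence that anxiety does not explain a blood pressure result. With these directions, such a finding could come from the form and not from the participants.

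**Working it through.** The documents give no hypothesis, analysis or power statement for state anxiety, so there is no figure to reproduce. The check has two parts: a comparison of the texts, and an illustration of what the wording could do.

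**Texts side by side**

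- Directions: a character-by-character comparison of the full printed directions on the two forms shows that they are identical. Both give the general time frame in the first sentence and again in the last.
- Use: the state form is completed under four conditions; the trait form is completed once, at visit 4.
- Items and scale: these differ. The state form uses an intensity scale and the trait form a frequency scale. State item 7 has a present time frame of its own: "I am presently worrying over possible misfortunes". The state form's directions therefore conflict with one of its own items as well as with its schedule.
- Which text participants saw: the supplement offers electronic completion for the trait and expectations forms but not for the state form. The REDCap record view marks the revised trait form and the expectations form as surveys, and does not so mark State V1 to V4. The visit 2 and visit 3 checklists have staff hand over the night-time form. This suggests that participants read the printed form, but the REDCap state screens are not reproduced and cannot be checked.

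**Illustration (assumptions mine)**

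Let f be the share of participants who take the directions literally, so that their answers do not shift with condition. The expected mean difference is then (1 − f) times the true one. Taking the research plan's 600 completers, two-sided 5% level and 80% power (section D.12.1), the smallest true paired difference that can be detected, in SDs of the within-person difference, is

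(1.960 + 0.842) / √600 / (1 − f) = 0.114 / (1 − f).

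| f | Share of true difference retained | Detectable true difference (SD) |
|---|---|---|
| 0 | 1.00 | 0.11 |
| 0.25 | 0.75 | 0.15 |
| 0.50 | 0.50 | 0.23 |
| 0.75 | 0.25 | 0.46 |
| 0.90 | 0.10 | 1.14 |

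The SD is held fixed, which supposes that literal responders still show ordinary scatter between completions. If their answers were exactly identical each time, the SD would shrink and the loss of power would be smaller, but the attenuation of the mean would be the same. The documents give no value for f. The contrast is lost altogether only as f approaches 1.

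**The case against.** A reader might infer that the form cannot show any difference between conditions and is simply the trait scale given four times. The documents do not support that. The two forms share only their directions. The state items, the word for the present in item 7, the intensity scale and the setting in which the form is filled in may all draw momentary answers from some participants. Sensitivity is reduced by an unknown amount; it is not shown to be nil.

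A reader might also infer that every state-anxiety contrast is uninterpretable. The likely bias runs towards no difference, so it is a null result that becomes ambiguous. An observed difference would still carry information, though probably understated.

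It is also fair to say that the damaged comparison is inferred from the schedule. The supplement gives timing only. No table in the analysis plan uses the state score. The research plan names only the trait scale (section D.8.3.2) and lists anxiety as an adjustment covariate without reference to the state form (section D.11.2). This limits the importance of the point but does not answer it, because four condition-linked completions have little purpose if answers are not meant to vary.

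Finally, the electronic wording is unknown. The REDCap trait screen described in the manual does not reproduce the printed trait directions exactly, so the state screens cannot be assumed to match the paper form. The point is confined to the printed form.

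**Conclusion.** The point holds as a minor one. The printed state form has the wrong time frame for the use the supplement makes of it, and following it literally biases differences between conditions towards zero. The size depends on how many participants answered literally, which the documents do not reveal: the table runs from no loss to 90% of the difference lost.

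The conclusion rests on two assumptions: that participants read the printed directions, and that the repeated completions were meant to separate the conditions. The first is suggested by how the form is handed out, and the second by the schedule; neither is stated outright. A reader should not extend the point to Aims 1 to 3, whose hypotheses, analyses and sample size do not use the state score.

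**What to change.** Change both sentences of the state form's directions to ask how the participant feels right now, at this moment. Check whether the REDCap State Anxiety Inventory V1 to V4 screens carry the same error, and correct them if so. Make any change between participants, never within one participant's four completions, so that each person's comparison uses a single wording. Record which version each participant completed.

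The analysis plan's Table 1 already reports 603 participants, so for most or all of the data the practical step is labelling. Describe the scores as obtained under directions about general feeling, state the limitation wherever they are reported, and do not read a null contrast as evidence that state anxiety is the same across conditions.

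The cost is two sentences on one form, a check of four screens and a version field. The one downside is that a change during data collection leaves two form versions to be distinguished in any analysis.
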